#### 14.1.1 PRE-CAE® INFERIOR FLUORESCEIN STAINING

Pre-CAE® fluorescein staining in the inferior region of the cornea will be graded using the Ora Calibra® Corneal and Conjunctival Staining Scale. The Ora Calibra® Corneal and Conjunctival Staining Scale ranges from 0 to 4 [REDACTED], where grade 0 = none, [REDACTED] and 4 = severe.

Changes from baseline in the pre-CAE® inferior fluorescein staining scores will be summarized at Visit 6 (Day 57 ± 3) by treatment group for the study eye using quantitative summary statistics. Changes from baseline will be compared between each dose of 0.25% and 0.10% HL036 Ophthalmic Solution and placebo using an ANCOVA model that adjust for baseline and site. In addition, the study site by treatment interaction will be explored in a separate model to evaluate how the treatment effect may differ across study sites. In the case of a significant interaction at the 0.05 level, analyses will be performed by site to understand how the treatment effect differs across sites. The differences in means, two-sided 95% confidence intervals (CIs) for the difference in means and p-values will be reported. Pairwise t-tests from the ANCOVA model will be used to compare treatment and placebo groups. In addition, subjects in either active treatment group will be compared to the placebo group using a separate ANCOVA model.

T-tests and Wilcoxon rank sum tests will also be conducted as sensitivity analyses to assess robustness of the results.

The primary analysis will use MCMC imputation to have a full accounting of the ITT population at Visit 6 (Day 57 ± 3). The MCMC method will be performed using the SAS procedure PROC MI. The SAS code for obtaining multiple imputation data is:

```
PROC MI DATA = INDATA SEED = 425754 OUT = OUTDATA NIMPUTE = 20
      MINIMUM = 0 MAXIMUM = 4 ROUND = 0.5;
      BY TREATMENT SITE;
      MCMC INITIAL = EM;
      VAR BASELINE INFERIOR;
      RUN;
```

where

- *INDATA* is the name of the input dataset
- *OUTDATA* is the name of the output dataset
- *TREATMENT* is the name of the treatment group variable
- *SITE* is the site id
- *BASELINE* is the baseline pre-CAE® inferior fluorescein staining score in the study eye
- *INFERIOR* is the pre-CAE® inferior fluorescein staining in the study eye at Visit 6 (Day 57 ± 3)

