After obtaining twenty complete data sets and calculating changes from baseline, the following SAS code will be used to run the ANCOVA model on each data set and combine the results from the twenty analyses:

```

PROC MIXED DATA = OUTDATA;
  BY _IMPUTATION_;
  CLASS TREATMENT SITE;
  MODEL CHANGE_INFERIOR = SITE BASELINE TREATMENT / SOLUTION COVB;
  LSMEANS TREATMENT / CL PDIFF;
  ODS OUTPUT LSMEANS = OUTLS DIFFS = OUTDIFFS;
RUN;
PROC SORT DATA=OUTLS; BY TREATMENT _IMPUTATION_; RUN;
PROC MIANALYZE DATA=OUTLS;
  BY TREATMENT;
  MODELEFFECTS ESTIMATE;
  STDERR STDERR;
RUN;

DATA OUTDIFFS;
  SET OUTDIFFS;
  COMPARISON = TREATMENT || ' - ' || LEFT(_TREATMENT);
RUN;
PROC SORT DATA=OUTDIFFS; BY COMPARISON _IMPUTATION_; RUN;
PROC MIANALYZE DATA=OUTDIFFS;
  BY COMPARISON;
  MODELEFFECTS ESTIMATE;
  STDERR STDERR;
RUN;

```

where

- *TREATMENT* is the name of the treatment group variable
- *SITE* is the site id
- *BASELINE* is the baseline pre-CAE® inferior fluorescein staining score in the study eye
- *CHANGE\_INFERIOR* is the pre-CAE® inferior fluorescein staining in the study eye at Visit 6 (Day 57 ± 3) – *BASELINE*
- *OUTLS* is the name of the output dataset that contains the statistical results for the treatment means from the ANCOVA model that is run on each of the twenty imputation datasets
- *OUTDIFFS* is the name of the output dataset that contains the statistical results for the differences in treatment means from the ANCOVA model that is run on each of the twenty imputation datasets

Similar SAS code will be used to conduct MCMC multiple imputation analysis for T-tests.

A sensitivity analysis will be performed on the ITT population using control-based pattern mixture model imputation. The SAS code for obtaining multiple pattern mixture model imputation data is:

```

PROC MI DATA = INDATA SEED = 386922 OUT = MDATA NIMPUTE = 1
  MINIMUM = 0 MAXIMUM = 4 ROUND = 0.5;

```

```

MCMC IMPUTE=MONOTONE;
VAR BASELINE INFERIOR;
RUN;

PROC MI DATA = MDATA SEED = 253464 OUT = OUTDATA NIMPUTE = 20
      MINIMUM = . . 0 0 MAXIMUM = . . 4 4 ROUND = . . 0.5 0.5;
CLASS SITE TREATMENT;
MONOTONE REG(INFERIOR = BASE SITE / DETAILS);
MNAR MODEL(INFERIOR / MODELOBS=(TREATMENT='Placebo')) ;
VAR SITE TREATMENT BASELINE INFERIOR;
RUN;

```

where

- *INDATA* is the name of the input dataset
- *MDATA* is the name an intermediary dataset with a monotone missing pattern
- *OUTDATA* is the name of the output dataset
- *TREATMENT* is the name of the treatment group variable

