#### 14.1.2 ORA CALIBRA® OCULAR DISCOMFORT SCALE

Ocular discomfort scores will be subjectively graded by the subjects using the Ora Calibra® Ocular Discomfort Scale at all scheduled visits. The ocular discomfort scale ranges from 0 to 4 [REDACTED]

[REDACTED]  
 [REDACTED].

Changes from baseline in the pre-CAE® Ocular Discomfort Scale will be summarized at Visit 6 (Day 57 ± 3) by treatment group for the study eye using quantitative summary statistics. Changes from baseline will be compared between each dose of 0.25% and 0.10% HL036 Ophthalmic Solution and placebo using an ANCOVA model that adjust for baseline and site. In addition, the study site by treatment interaction will be explored in a separate model to evaluate how the treatment effect may differ across study sites. In the case of a significant interaction at the 0.05 level, analyses will be performed by site to understand how the treatment effect differs across sites. The differences in means, two-sided 95% confidence intervals (CIs) for the difference in means and p-values will be reported. Pairwise t-tests from the ANCOVA model will be used to compare treatment and placebo groups. In addition, subjects in either active treatment group will be compared to the placebo group using a separate ANCOVA model. T-tests and Wilcoxon rank sum tests will also be conducted as sensitivity analyses to assess robustness of the results.

The primary analysis will use MCMC imputation on the ITT population at Visit 6 (Day 57 ± 3). SAS code for the multiple imputation analysis will resemble the code in Section 14.1.1. for pre-CAE® inferior fluorescein staining. Sensitivity analyses will be performed on the ITT and PP populations using observed data only, and on the ITT population using LOCF methodology and pattern mixture model imputation. The sensitivity analyses will include comparisons between treatment and placebo groups using ANCOVA models adjusting for site and baseline and t-tests. Observed data only (ITT and PP) and LOCF analyses will also include Wilcoxon rank sum tests.

Changes from baseline in the pre-CAE® Ocular Discomfort Scale in the study eye will be displayed graphically in a bar chart with standard error bars by visit and treatment group.

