#### 14.2.1 FLUORESCEIN STAINING

Corneal and conjunctival fluorescein staining will be performed at all scheduled visits, on both eyes and graded using the Ora Calibra® Corneal and Conjunctival Staining Scale. Both pre- and post-CAE® assessments will be made at Visits 1, 2, 4, 5, and 6. The scale will grade the cornea and conjunctiva by five regions: inferior, superior, central, temporal, and nasal. The Ora Calibra® Corneal and Conjunctival Staining Scale ranges from 0 to 4 [REDACTED], where grade 0 = none, [REDACTED] and 4 = severe.

Fluorescein staining scores will be summarized by visit, time point (pre- and post-CAE®), and region (5 regions, plus corneal sum, conjunctival sum, and total scores) for the study eye using quantitative summary statistics. The corneal sum score will be the sum of scores from the inferior, superior, and central regions. The conjunctival sum score will be the sum of scores from the nasal and temporal regions. The total score will be the sum of scores from all five regions.

Pairwise two-sample t-tests will be employed to compare treatment and placebo means at each visit and time point. Comparisons between treatment groups and between all active groups and placebo will also be conducted. The differences in means, two-sided 95% confidence intervals (CIs) for the difference in means and p-values will be reported. Wilcoxon rank sum tests will also be conducted. Analyses will be performed on the ITT population with observed data only.

Changes from baseline will be compared between treatment groups using ANCOVA models that adjust for baseline and site. The differences in means, two-sided 95% confidence intervals (CIs) for the difference in means and p-values will be reported. T-tests and Wilcoxon rank sum tests will also be conducted. Analyses will be performed on the ITT population with observed data only.

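### The primary multiple imputation uses only baseline and the Visit 6 score, so it nearly repeats the observed-data ANCOVA and ignores interim scores that could remove a small, conditional dropout bias

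*SAP*

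**What the plan says.** SAP 14.1.1 states that "The primary analysis will use MCMC imputation to have a full accounting of the ITT population at Visit 6". The printed PROC MI step runs "BY TREATMENT SITE" with "VAR BASELINE INFERIOR", where the last variable is the pre-CAE staining score at Visit 6. It makes 20 imputations, bounded to 0–4 and rounded to 0.5. Each completed data set goes to an ANCOVA on site, baseline and treatment, the same model as the observed-data and LOCF analyses.

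For discomfort, SAP 14.1.2 prints no code but says that "SAS code for the multiple imputation analysis will resemble the code in Section 14.1.1".

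Interim scores exist for both endpoints. SAP 14.2.1 says "Corneal and conjunctival fluorescein staining will be performed at all scheduled visits", and 14.2.6 says the same of discomfort. SAP 9.3 pairs the Day 8 non-CAE score with the pre-CAE baseline, so Days 8, 15 and 29 all have a usable value.

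SAP 9.2 plans observed-data, LOCF and pattern-mixture analyses as checks. The pattern-mixture code regresses Visit 6 on baseline and site only: "MONOTONE REG(INFERIOR = BASE SITE / DETAILS", with "VAR SITE TREATMENT BASELINE INFERIOR" as its variable list.

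**The concern.** A subject whose score moved by Day 29 and who then left is imputed as if only the baseline were known. Imputing from baseline within arm and site, then fitting a model that already contains baseline and site, is close to analysing completers. Agreement between the primary and observed-data analyses would therefore say little about robustness.

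The interim scores matter because they are probably the only on-treatment efficacy data for early leavers. Protocol 4 asks these subjects for safety assessments. Protocol 5.5 refers to a termination visit, but no list of its tests is printed. Protocol 5.5 also gives the need for prohibited medication as a possible reason for withdrawal, which is a plausible link between worse scores and leaving.

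The direction depends on the pattern. If worse scores raise the chance of leaving under one rule in all arms and the drug works, more placebo subjects leave and the estimate moves toward the null. If the dependence exists in one arm only, the bias can go either way. SAP 9.5 requires all four tests (sign and symptom, both doses) to be significant. Bias toward the null in any one test therefore costs power, whereas a drug-favouring bias in one contrast cannot by itself create a false success.

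**Working it through.** **Inputs from the documents.** SAP 6: 50 per arm, 10% dropout, 45 completers; staining effect 0.5 with SD of change 0.72; discomfort effect 0.80 with SD 1.15; 90% power per comparison. SAP 9.4: two-sided 0.05. Protocol synopsis: up to 3 sites.

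**The plan's own figures.** The two-sample t-test with 45 per group gives power 90.3% (staining) and 90.4% (discomfort). 0.9² = 81% and 0.9⁴ = 65.6%. The stated 90%, 81% and 66% are reproduced.

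**Assumed, because the documents give no between-visit correlations and no dropout timing or pattern.** Negative differences favour the drug.

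**1. Large-sample approximation.** With dropout fraction d, partial correlation ρ between the interim and Visit 6 scores given baseline, and leavers shifted by k SDs, the bias from one affected arm is about d/(1−d) × ρ × SD × k.

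- Staining, d = 0.10: from 0.111 × 0.3 × 0.72 × 0.5 = 0.012 to 0.111 × 0.7 × 0.72 × 1.0 = 0.056, that is 2–11% of 0.5.
- Discomfort: from 0.111 × 0.3 × 1.15 × 0.5 = 0.019 to 0.111 × 0.7 × 1.15 × 1.0 = 0.089, that is 2–11% of 0.80.
- Opposite patterns in the two arms double these figures.

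**2. Simulation.** 400 trials per scenario, 50 per arm, 3 equal sites, 20 imputations. SD of change and effect match the plan after bounding and rounding. Baseline–Day 57 correlation 0.5, Day 29–Day 57 correlation 0.7, effect growing linearly over the visits. Dropout 10%, either all after Day 29 or spread over Days 8, 15 and 29. The odds of leaving are multiplied by 2.7 or 7.4 per SD of the last score. Bias is measured against the complete-data ANCOVA on the same trials (Monte Carlo SE at most 0.003 for staining and 0.004 for discomfort).

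| Dropout pattern | Staining: bias of SAP imputation | Discomfort: SAP imputation minus imputation with interim visits |
|---|---|---|
| Random, or equal in all arms | +0.002 to +0.007 | −0.005 to +0.003 |
| One common rule, drug works | +0.013 to +0.032 | +0.008 to +0.033 |
| Score-dependent in active only | −0.021 to −0.041 | −0.023 to −0.059 |
| Score-dependent in placebo only | +0.030 to +0.053 | +0.025 to +0.056 |

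For staining, imputation with interim visits has bias −0.002 to +0.006 in the same cases. Discomfort is shown as a gap because keeping values within 0–4 shifts both methods by about +0.01 to +0.02 even under random dropout. The standard errors are about 0.13 (staining) and 0.20 (discomfort), so 0.053 is about 0.4 SE (0.053/0.13) and 11% of the effect (0.053/0.5).

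**3. Near-repetition of the observed-data analysis (staining).** The SAP imputation minus the observed-data ANCOVA is 0.000 to +0.006 on average and 0.013–0.017 per trial. In a second simulation with other assumptions (between-visit correlations 0.45–0.60), the two estimates correlated at 0.98–0.99.

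**4. Power per staining comparison, SAP imputation against interim visits added.** Common rule: 94.0–95.6% against 96.1–97.1%. Placebo only: 90.2–95.4% against 95.1–96.8%. The two methods reach different significance conclusions in 0.7–4.9% of comparisons. With no drug effect, rejection stays at 4.8–5.6%.

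**5. Range (staining, SAP imputation, dropout after Day 29, odds multiplier 2.7).**

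| Setting | Active only | Placebo only | Common rule |
|---|---|---|---|
| Correlation 0.55 | −0.017 | +0.024 | +0.014 |
| Correlation 0.85 | −0.038 | +0.042 | +0.020 |
| Dropout 5% | −0.012 | +0.017 | +0.008 |
| Dropout 20% | −0.055 | +0.072 | +0.026 |

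Opposite patterns by arm, an extreme case, give sizes of 0.049 to 0.102 at 10% dropout. The second simulation gave 0.059 for opposite patterns, reduced to 0.010 by the interim visits, with power 87% against 94%.

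**6. Planned sensitivity analyses (staining bias).** LOCF uses interim scores but has its own bias: +0.012 to +0.027 under random dropout and +0.032 to +0.065 for active only. The control-based pattern-mixture analysis is at about +0.05 under random dropout. It partly offsets a drug-favouring bias when the drug works (+0.013 to +0.028, active only). It does not when there is no effect (−0.025, against −0.028 for the SAP imputation), and it enlarges the placebo-only bias to +0.074 to +0.094.

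**The case against.** The strongest reply is that the effect is too small and too hypothetical to act on. The documents give one overall dropout figure and no evidence that leaving depends on scores or does so differently by arm. The simulated odds multipliers of 2.7 and 7.4 per SD are strong. At 1.25 to 1.5, a large-sample calculation gives only about 0.007–0.013 for one affected arm and 0.001–0.002 under a common rule. Simulated power stays at or above the planned 90% outside the opposite-pattern case, with a Monte Carlo error of about one percentage point. SAP 9.5 calls the trial primarily exploratory, and four missing-data approaches are already planned. Baseline-plus-endpoint imputation is valid if leaving depends only on baseline, arm and site. For discomfort, the variable list is inferred from a cross-reference.

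All of this stands as a limit on size, and the ranges above should be read with it. It does not remove the point. The imputation is meant to account for missing data and, as coded, adds almost nothing to a completer analysis. The planned checks do not fill the gap, and the unused data are already in the database. The cross-reference to the staining code is most naturally read as covering both endpoints.

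**Conclusion.** The concern holds. As printed for staining, and by reference for discomfort, the primary imputation omits the interim scores and nearly reproduces the observed-data ANCOVA.

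The consequence is conditional and small: at most about 0.4 SE for staining at 10% dropout outside the opposite-pattern case, less if the dependence is mild, and close to zero if dropout is random or alike in all arms. The main risk is lost power in a design that needs four significant results and has a planned joint power of 66%; false-positive rates are not materially raised. The sizes rest on the assumed correlations, dropout timing and strength of dependence. Adding interim scores removes most of the bias when leaving depends on observed scores, but would not cure dropout driven by unobserved ones. The change is worth making because it is cheap; the plan does not fail without it.

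**What to change.** Before unmasking, for both coprimaries:

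- Run the primary PROC MI by treatment only. The variable list becomes site indicators (one fewer than the number of enrolling sites), baseline, Day 8 (non-CAE), and Days 15, 29 and 57 (pre-CAE).
- Give the minimum, maximum and rounding options as lists in that order: a dot for each site indicator, then each scale's own limits and increment. Print the discomfort code in full.
- Keep the ANCOVA and the combining step unchanged.

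Site has to leave the BY statement because an arm-by-site cell holds only about 50/3, or 16–17 subjects, too few for a five-variable model.

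Leave the assumption of the control-based pattern-mixture analysis as it is, and only correct the regressor `BASE` to `BASELINE`, the name in its variable list. A pattern-mixture version with interim visits, if wanted, should be a separate, declared analysis, because it is less conservative: under random dropout its shift toward the null is +0.028 to +0.040 instead of about +0.05 for staining, and +0.048 to +0.063 instead of about +0.08 for discomfort.

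The cost is a few lines of code and SAP wording, with no new data. Protocol 10.4.3 names MCMC imputation without a variable list, so the change stays within it. The downside is a larger model, about 7 variables on about 45 completers per arm. Even so, under random dropout the simulated standard error fell by 2.1–2.7% for staining and 1.1–1.4% for discomfort.

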TITLE OF STUDY: A Phase 2, Multicenter, Randomized, Double-Masked and Placebo-Controlled Study Evaluating the Efficacy of Two Concentrations (0.10% and 0.25%) of HL036 Ophthalmic Solution Compared to Placebo in Subjects Diagnosed with Dry Eye	
PROTOCOL NUMBER:	HL036-DED-US-P201
STUDY SITES:	Multicenter study involving up to 3 sites located in the United States
STUDY PERIOD: Approximately 70 days	PHASE OF DEVELOPMENT: Phase 2
STUDY FORMULATIONS:	0.10% HL036 Ophthalmic Solution 0.25% HL036 Ophthalmic Solution Placebo Vehicle Solution
OBJECTIVE: The objective of this study is to compare the safety and efficacy of 0.10% and 0.25% HL036 Ophthalmic Solutions to placebo for the treatment of the signs and symptoms of dry eye.	
DOSE, ROUTE AND REGIMEN: Screening: Between Visits 1 and 2, all subjects will receive 14 consecutive days (\pm 2) of open-label placebo ocular drops self-administered BID in both eyes in the morning and the evening. Treatment: During the 8-week (56 ± 2 days) treatment period, HL036 Ophthalmic Solution at concentrations of 0.25%, 0.10% or placebo solution will be administered BID by bilateral topical ocular dosing. Subjects will be randomized to one of three treatment arms (1:1:1) to receive study drug administered by trained study personnel after the Post-CAE® #2 assessments at Visit 2.	
DURATION OF TREATMENT: Approximately 56 days (8 weeks)	
REFERENCE THERAPY, DOSE, ROUTE AND REGIMEN: Open-label placebo solution (placebo) will be provided to subjects from Day -14 to Day 0. Placebo ocular drops will be self-administered BID in both eyes in the morning and the evening. Following randomization, placebo will be dosed according to the same schedule as the HL036 Ophthalmic Solution concentrations.	
NUMBER OF SUBJECTS PLANNED: Approximately 150 subjects will be enrolled in the study. The total number of expected participants, including screen failures, is approximately 375 subjects.	

DIAGNOSIS AND ALL CRITERIA FOR INCLUSION AND EXCLUSION:

INCLUSION CRITERIA:

Individuals eligible to participate in this study must meet all of the following criteria:

1. Be at least 18 years of age;
2. Provide written informed consent;
3. Be willing and able to comply with all study procedures;
4. Have a patient-reported history of dry eye for at least 6 months prior to enrollment;
5. Have a history of use or desire to use eye drops for dry eye symptoms within 6 months of Visit 1;

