## 6. Sample Size and Power Considerations

The primary objective of the study is to demonstrate a statistically significant difference between the active treatments and placebo.

This study is expected to enroll 50 subjects in each of the three treatment arms, for a total of 150 randomized subjects. Assuming a 10% drop out rate, 45 subjects per group are expected to complete the study.

Assuming a common standard deviation in the change from baseline for the pre-CAE® inferior corneal fluorescein staining of 0.72 units, a sample size of 45 subjects per group will have 90% power to detect a difference of 0.5 units between each of the active treatment groups and the placebo group using a two-sample t-test at a significance level of 0.05. A sample size of 45 subjects per treatment arm will have 90% power to detect a mean difference of 0.80 units in the change from baseline for the pre-CAE® ocular discomfort as assessed by the Ora Calibra® Ocular Discomfort Scale, assuming a standard deviation of 1.15 units. Using an analysis of covariance model (ANCOVA) for each primary

endpoint should yield standard deviations no greater than those from a two-sample t-test. Therefore, the power for each endpoint for both the sign and the symptom is 81%, assuming independence between the endpoints. The power for both the sign and the symptom in both active treatments is 66%, assuming independence of treatments.

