### 9.4 Data Analysis Conventions

All data analysis will be performed by SDC after the study is completed and the database has been locked and released for unmasking. Statistical programming and analyses will be performed using SAS® Version 9.4 or higher. Output will be provided in RTF (Rich Text Format) for tables and PDF (Portable Document Format) for tables, listings, and figures using landscape orientation. All study data will be listed by subject, treatment, and visit (as applicable) based on all enrolled subjects unless otherwise specified.

All summaries will be presented by treatment group and visit where appropriate, unless otherwise specified. Summaries will be provided for demographics, baseline medical history, concurrent therapies, and subject disposition. For the purpose of summarization, medical history, concurrent therapies, and adverse events will be coded to Medical Dictionary for Regulatory Activities (MedDRA) and World Health Organization (WHO) Drug dictionaries, as appropriate.

Summaries for continuous and ordinal variables will include the number of observations (n), arithmetic mean, standard deviation (SD), median, minimum, and maximum. Minima and maxima will be reported with the same precision as the raw values; means and medians will be presented to one additional decimal place than reported in the raw values. Standard deviations will be presented to two additional decimal places than reported in the raw values. Summaries for discrete variables will include frequency counts and percentages. All percentages will be rounded to one decimal place (i.e., XX.X%).

All statistical tests will be two-sided with a significance level of 0.05 ( $\alpha = 0.05$ ) unless otherwise specified. Confidence intervals (CI) for differences between treatment groups will be two-sided at 95% confidence levels where appropriate. All p-values will be rounded to four decimal places; p-values

less than 0.0001 will be presented as "<0.0001"; p-values greater than 0.9999 will be presented as ">0.9999".

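### The code that pools the primary analysis omits the complete-data degrees of freedom, so co-primary intervals are about 1% narrower and p-values slightly smaller than the correct reference distribution gives

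*SAP*

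**What the plan says.** SAP section 14.1.1 makes multiple imputation with 20 data sets the primary method. It imputes separately within each treatment-by-site cell, fits an ANCOVA with site, baseline and treatment to each completed data set, and pools the results with two PROC MIANALYZE calls. One call pools the treatment means. The other, "PROC MIANALYZE DATA=OUTDIFFS", pools the differences that decide the trial. Each contains only BY, MODELEFFECTS and STDERR statements. Neither has EDF=, and the degrees of freedom from PROC MIXED are not passed on.

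The same section says that treatment and placebo are compared by pairwise t-tests from the ANCOVA. The code extends beyond this endpoint:

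- For the t-tests on imputed data: "Similar SAS code will be used to conduct MCMC multiple imputation analysis for T-tests".
- The pattern-mixture results are analysed in the same way as the MCMC results (14.1.1).
- The ocular discomfort code is to resemble the staining code (14.1.2).

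SAP section 9.4 sets the level: "All statistical tests will be two-sided with a significance level of 0.05". Neither document supplies a small-sample adjustment elsewhere.

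**The concern.** A pooled analysis with some data missing cannot carry more information than the same analysis with all data present. As printed, the code allows it to: the pooled test is referred to a t distribution that is almost normal, with many more degrees of freedom than the complete-data model has. This departs from the ANCOVA t-tests that the text promises. It also means that the primary analysis is judged against a different reference distribution from the observed-data and LOCF analyses, which take their tests directly from PROC MIXED with finite df.

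The direction favours the active arms. Success needs both endpoints significant for both doses (SAP section 9.5), so all four deciding comparisons are affected. If a p-value fell just under 0.05, correcting the code after unmasking would look like a post hoc change.

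**Working it through.** **The plan's own figures.** The inputs in SAP section 6 are "This study is expected to enroll 50 subjects in each of the three treatment arms, for a total of 150 randomized subjects" and "Assuming a 10% drop out rate, 45 subjects per group are expected to complete the study". For the sign, the plan gives an SD of 0.72 and "90% power to detect a difference of 0.5 units between each of the active treatment groups and the placebo group". With 45 per arm, two-sided 0.05 and 88 df, the noncentral t gives 90.3% for the sign (0.5/0.72) and 90.4% for the symptom (0.80/1.15). Then 0.9² = 81% and 0.9⁴ = 65.6%, stated as 66%. All reproduce. The plan states no pooled df or critical value.

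**Inputs for the df check.**
- m = 20 imputations (SAP 14.1.1).
- N = 150 (SAP section 6).
- Sites: up to three (Protocol synopsis). With three, the ANCOVA has 6 parameters: intercept, baseline, two for site and two for treatment. Complete-data residual df: v0 = 150 − 6 = 144. With two sites it is 145, with one 146.
- λ, the share of total variance due to missing data, is not in the documents. I assume 0.10, in line with 10% dropout, and show 0.02 to 0.30.
- That PROC MIANALYZE takes the complete-data df as infinite when EDF= is absent is a property of the software, not something the documents state.

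**Formulas.**
- Without EDF= (Rubin): vm = (m − 1)/λ².
- With EDF= (Barnard–Rubin): vobs = [(v0 + 1)/(v0 + 3)] × v0 × (1 − λ), and df = 1/(1/vm + 1/vobs).

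**At λ = 0.10.** vm = 19/0.01 = 1,900. vobs = (145/147) × 144 × 0.90 = 127.8. df = 1/(1/1,900 + 1/127.8) = 119.8. The two-sided 5% critical values are 1.9612 and 1.9800. The ratio 1.9800/1.9612 = 1.0096, so the correct interval is 0.96% wider.

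| λ | df without EDF= | df with EDF=144 | critical value without | critical value with | correct interval wider by | reported p of 0.0500 becomes |
|---|---|---|---|---|---|---|
| 0.02 | 47,500 | 138.8 | 1.960 | 1.977 | 0.88% | 0.0520 |
| 0.05 | 7,600 | 132.6 | 1.960 | 1.978 | 0.91% | 0.0521 |
| 0.10 | 1,900 | 119.8 | 1.961 | 1.980 | 0.96% | 0.0522 |
| 0.20 | 475 | 91.7 | 1.965 | 1.986 | 1.08% | 0.0524 |
| 0.30 | 211 | 67.6 | 1.971 | 1.996 | 1.24% | 0.0528 |

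**Where a verdict could change.** At λ = 0.10, a statistic equal to 1.980 is reported on 1,900 df as p = 0.048. Only reported p-values between about 0.048 and 0.050 change sides.

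**Power.** For the sign, the noncentrality is 0.5/(0.72 × √(2/50)) × √0.90 = 3.294. Power is 90.8% with the cut-off of 1.961 and 90.4% with 1.980, a loss of about 0.3 points before rounding.

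**MI t-tests.** Two arms of 50 give v0 = 98. At λ = 0.10 the df is 82.7 and the critical value 1.989. Intervals from the printed code are 1.4% too narrow against that reference, and a reported 0.0500 becomes 0.0532.

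**Actual error rate.** I used null simulations of the plan's within-cell imputation and ANCOVA: 12,000 trials per setting, two comparisons each, Monte Carlo SE 0.0015. Assumptions: data missing completely at random, three equal sites, baseline-to-Visit 6 correlation 0.5, SD 0.72, mean 2, scores in half-point steps.

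| missing | type I error without EDF= | with EDF=144 |
|---|---|---|
| 5% | 0.048 | 0.047 |
| 10% | 0.048 | 0.046 |
| 20% | 0.043 | 0.040 |

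At 10% missing, the two versions gave different verdicts in 0.22% of comparisons. Further runs gave 0.046 to 0.049 without EDF= at 10% missing, and 0.049 to 0.053 at 2% to 5%.

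**The case against.** The best case for leaving the code alone has four parts.

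- **No loss of error control is demonstrated at the planned dropout.** A reader might infer that the true size of each co-primary test is 0.0522, or that every co-primary interval undercovers. The documents do not support that. The figure 0.0522 assumes that the pooled statistic follows the adjusted t distribution exactly. The plan imputes within treatment-by-site cells (about 17 subjects each if there are three equal sites), and this widens the pooled variance. At 10% missing the simulated size is already below 0.05, and EDF= lowers it further. This part stands. But the offset is accidental: it comes from simulated scenarios, it was less reliable at 2% to 5% missing, and a better imputation model could remove it. It does not justify the wrong reference distribution.
- **By-site analyses.** A reader might also infer a larger distortion there: about 50 subjects, 46 df, and a reported 0.0500 becoming 0.057. The SAP plans by-site analyses only after a significant interaction, to understand it. It does not say that they use imputation or this code, and sites of 50 assume three equal centres. This part stands.
- **Cross-checks exist.** The observed-data and LOCF ANCOVAs use finite df and are tabulated beside the primary result, so a borderline finding would be visible. True, but they are sensitivity analyses and do not decide success.
- **The matter is small.** Rubin's large-sample rule is a recognised rule, the SAP calls the trial primarily exploratory, and four tests must all succeed. All true. This limits the importance of the point without making the code right.

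**Conclusion.** The point holds as a minor error in the specification. The pooled co-primary comparisons use more degrees of freedom than complete data could supply, contrary to the ANCOVA t-tests stated in the same section. Measured against the correct reference distribution, intervals are about 1% narrower and a reported p of 0.0500 corresponds to about 0.0522. The effect is slightly larger for the MI t-tests. Inflated overall type I error is not shown for the primary ANCOVA at 10% dropout and should not be claimed.

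This rests on the software default when EDF= is absent, on 150 subjects at three sites, and on an assumed missing information of 10%. The conclusion hardly changes from 2% to 30%.

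**What to change.** Before unmasking, amend the PROC MIANALYZE calls in SAP section 14.1.1, and the code derived from them, to include EDF= set to the residual df of the complete-data model:

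- ANCOVA for both co-primary endpoints and for the pattern-mixture analysis: N minus the number of model parameters, which is 144 for 150 subjects and three sites. State it as a rule so that it follows the actual N and number of sites.
- Two-arm t-tests on imputed data: about 98.
- By-site models: the matching residual df, only if they are run with this imputation code.

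The change is one option per call and needs no extra subjects. P-values become very slightly less favourable, and power for the sign falls by about 0.3 points.
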